8.3.4. Analysis of CBR and iCBR

The number and percentage of subjects with CBR3, CBR6, CBR9, iCBR3, iCBR6, iCBR9, and their 95% confidence intervals will be estimated with Clopper-Pearson method.

8.3.5. Analysis of Time to Events

Time to event parameters (DoR, iDoR, PFS, iPFS, OS) will be estimated using the Kaplan-Meier method (Kaplan & Meier, 1958). The number and percentage of subjects with events/censored, the 1st quartile (25%), median, 3rd quartile (75%), and their 2-sided 95% confidence interval, event-free rate at 3/6/9/12/15 months and their 2-sided 95% confidence interval will be presented.

Event or censor category of each subject in the summary for DoR, iDoR, PFS, iPFS will be presented. Event categories include progression and death. Censor categories include No progression and death, Progression or death after antineoplastic therapy, Progression or death after two or more missing assessment.

Kaplan-Meier curves for PFS, iPFS and OS of expansion cohorts will be plotted.

8.4. Subgroup Analyses

No subgroup analysis is planned.

9. Safety Analyses

9.1. Overview of Planned Safety Analyses

The Safety Analysis Set will be used to evaluate all safety endpoints unless otherwise specified. In particular, the DLT-Evaluable Analysis Set will be used to evaluate DLT endpoint and to estimate MTD.

Table 2 Overview of Planned Safety Analyses

	Data Displays Generated		
	Table	Figure	Listing
Maximum Tolerated Dose (MTD) and Dose Limiting Toxicity (DLT) Events			
Number and percentage of subjects having experienced DLT events	Y		Y
Adverse Events			
Overview of TEAEs	Y		
All TEAEs	Y		
TEAEs related to each study drug	Y		
All Serious TEAEs	Y		
Serious TEAEs related to each study drug	Y		
Grade 3 or higher TEAEs	Y		
Grade 3 or higher TEAEs related to each study drug	Y		
TEAEs leading to any study drug modification	Y		
TEAEs leading to deaths	Y		
TEAEs of Special Interest	Y		
Immune Related Adverse Event (irAE)	Y		Y
Infusion Related Reaction (IRR)	Y		Y
Cytokine Release Syndrome (CRS)	Y		Y
TEAEs leading to any study drug discontinuation	Y		Y
All Serious TEAEs during screening period(s)			Y

QMS Document Name: Statistical Analysis Plan Template(EN)	Page 22 of 41
QMS No (include version ref): STF-015-GL.03	Document date: 14JUL2022
CONFIDENTIAL	

	Data Displays Generated		
	Table	Figure	Listing
Primary Cause of Deaths			
On study Deaths	Y		Y
Deaths within 28 days of last administration			
Deaths after 28 days since last administration			
Clinical Safety Laboratory Tests			
Hematology	Y		Y
Clinical Chemistry	Y		Y
Coagulation	Y		Y
Dipstick Urinalysis	Y		Y
ECGs			
Heart Rate (beats/min)	Y		Y
PR Interval (msec)			
QRS Interval (msec)			
QT Interval (msec)			
QTcF Interval (msec)			
• Highest post-baseline QTcF >450 msec			
• Highest post-baseline QTcF >480 msec			
• Highest post-baseline QTcF >500 msec			
• Maximum CFB of QTcF > 30 msec			
• Maximum CFB of QTcF > 60 msec			
Overall interpretation & Clinical Significance			Y
Vital Signs & Body Measurements			
Heart Rate (beats/min)	Y		Y
Systolic Blood Pressure (mmHg)			
Diastolic Blood Pressure (mmHg)			
Temperature (°C)			
Other Safety Data Listings			
Physical Examination			Y
ECOG Performance Status			Y
Pregnancies			Y

9.2. MTD and DLT Events

9.2.1. Dose Escalation and Determination of MTD

The dose escalation and determination of the MTD and/or recommended dose will be guided by a BLRM with overdose control (EWOC) (see protocol section 4.1.1, and appendix F). The starting dose and some of the provisional dose levels that could be evaluated during this study are described in protocol Table 1. The doses to be investigated are not limited to the provisional dose level listed in the table. The proposed dose escalation scheme for WTX-330 includes a dose level -1 with a 50% lower dose than the first dose level, in the event that the first dose level is not tolerated. Doses are selected based on patient safety data and are subject to satisfying the EWOC criteria under BLRM. The RDE will be determined by the Dose Escalation Committee (DEC) considering all available data and is not stipulated in this SAP.

9.2.2. DLT Events

The DLT will be listed using the DLT-evaluable set.

QMS Document Name: Statistical Analysis Plan Template(EN)	Page 23 of 41
QMS No (include version ref): STF-015-GL.03	Document date: 14JUL2022
CONFIDENTIAL	

9.3. Adverse Events (AEs)

Unless otherwise specified, adverse events will be summarized using frequency tables by System Organ Class (SOC) and Preferred Term (PT).

9.3.1. AE-related Definitions and Derivations

9.3.1.1. Coding and Grading

All adverse events (AEs) will be coded using MedDRA® 26.0 and will be graded according to the National Cancer Institute Common Terminology Criteria for Adverse Events (NCI-CTCAE) version 5.0 (see Subsection 15.1), except for Cytokine Release Syndrome which will be graded with American Society for Transplantation and Cellular Therapy (ASTCT) Grade.

If severity grading is missing, the event will be graded as severe (Grade 3) unless the event being recorded is leading to life-threatening or death and will be graded accordingly as Grade 4 (life-threatening) or 5 (death).

9.3.1.2. Relatedness Assessment

The investigator will category the relatedness of AE to study drugs as 'Definite,' 'Probable,' 'Possible,' 'Unlikely,' and 'Unrelated.' In safety analyses, 'Definite,' 'Probable,' 'Possible' or missing relationship will be summarized as 'Related,' and other relationship will be treated as 'Unrelated.'

9.3.1.3. Treatment Emergent Adverse Events (TEAEs)

A TEAE is defined as an AEs that emerges or worsens (ie increase in CTCAE grade/ASTCT grade) on/after the first WTX-330 dose and within 30 days of the last WTX-330 dose or the start of a new cancer regimen, whichever occurs earlier.

9.3.1.4. TEAEs of Special Interest (AESIs)

TEAEs of special interest (AESIs) include

- >=Grade 2 CRS
- >= Grade 3 Oral Mucositis
- Hy's Law or >= Grade 3 increased ALT or AST

9.3.2. Planned Analysis of Adverse Events

Using the Safety Analysis Set, TEAE summaries will be presented by primary SOC and PT. Summaries will be presented by analysis groups described in Subsection 6.2. Although a PT or SOC may be reported more than once for a subject, each subject will only be counted once within the SOC or PT.

Number and percentage of subjects with the following TEAE categories will be presented in overview TEAE tables. Number and percentage of subjects with the following TEAE categories will be summarized by primary SOC and PT.

- All TEAEs
- TEAEs related to WTX-330
- All Serious TEAEs
- Serious TEAEs related to WTX-330
- Grade 3 or higher TEAEs
- Grade 3 or higher TEAEs related to WTX-330
- TEAEs leading to WTX-330 withdrawn
- WTX-330-related TEAEs leading to WTX-330 withdrawn

QMS Document Name: Statistical Analysis Plan Template(EN)	Page 24 of 41
QMS No (include version ref): STF-015-GL.03	Document date: 14JUL2022
CONFIDENTIAL	

- TEAEs leading to WTX-330 modification (including Dose Delayed, Dose Interrupted, Dose Reduced, Infusion Rate Reduced)
- WTX-330-related TEAEs leading to any study drug modification
- TEAEs leading to deaths
- TEAEs of Special Interest
- Immune Related TEAEs
- Infusion Related Reaction
- Cytokine Release Syndrome (CRS)
- DLT

The number and percentage of subjects with TEAEs, TEAEs related to each study drug, Serious TEAEs, Serious TEAEs related to each study drug will also be summarized by PT and/or SOC/PT/Maximum CTCAE/ASTCT Grade.

Subject listing(s) will be provided for subjects with all TEAEs, serious TEAEs, AESIs, Immune Related TEAEs, Infusion Related Reaction, Cytokine Release Syndrome, TEAE leading to death, TEAE leading to drug withdrawn, and TEAE leading to drug modification will be listed. All AEs will also be listed.

9.4. Deaths

The number and percentage of subjects who died on study, within 30 days *after* the last study drug administration day, and beyond 30 days *after* the last study drug administration, as well the number and percentage of subjects who died due to each primary cause will be summarized using the Safety Analysis Set.

Death details as collected in the eCRF will be listed.

9.5. Clinical Safety Laboratory Tests

For laboratory values in the form of $<x, \leq x$, below lower quantification limit, etc., the value will be imputed as $x/2$ or half of the lower quantification limit for the purpose of numerical descriptive summary. For laboratory values in the form of $>x, \geq x$, above upper quantification limit, etc., the value will be imputed as x or upper quantification limit for the purpose of numerical descriptive summary. When such imputation occurs, footnotes will be presented to clarify the imputation rule. The original laboratory values will be presented in data listings.

Hematology tests include Red blood cell (RBC) count, hemoglobin (Hb), hematocrit, mean corpuscular volume (MCV), mean corpuscular hemoglobin (MCH); white blood cell (WBC) count and differential count including, absolute lymphocyte count (ALC), and absolute neutrophil count (ANC), leukocytes with differential (manual microscopic review is performed only if WBC count and/or differential values are out of reference range); platelet count.

Clinical chemistry tests include Calcium, magnesium, potassium, sodium, bicarbonate, chloride phosphate, albumin, total blood urea nitrogen (BUN), C-reactive protein (CRP), creatinine, urate, estimated glomerular filtration rate, glucose, Alanine transaminase (ALT), aspartate transaminase (AST), bilirubin, alkaline phosphatase (ALP), lactic acid dehydrogenase (LDH), gamma-glutamyl transferase (GGT), Triiodothyronine (T3), thyroid-stimulating hormone (TSH), thyroxine (T4).

Coagulation laboratory tests Prothrombin time (PT) or International normalized ratio (INR), and Partial thromboplastin time (PTT) or Activated partial thromboplastin time (APTT).

Urinalysis tests include Dipstick (bilirubin, glucose, ketones, leukocytes, nitrite, occult blood, pH, protein, specific gravity, turbidity and colour, and urobilinogen) or microscopy.

QMS Document Name: Statistical Analysis Plan Template(EN)	Page 25 of 41
QMS No (include version ref): STF-015-GL.03	Document date: 14JUL2022
CONFIDENTIAL	

The value of hematology tests, coagulation tests, and chemistry tests will be graded with CTCAE 5.0. If a parameter includes both hypo- and hyper- CTCAE grade derivation, hypo- and hyper- will be derived separately. If the baseline is not CTCAE gradable (e.g., AST increase), the baseline measurement will be categorized as low/normal/high according to reference ranges.

- Quantitative laboratory data will be summarized using descriptive statistics (Subsection 15.2) of actual values and changes from baseline to each visit over time.
- Shift of the worst post-baseline CTCAE grade from baseline will be summarized as well.

Some tests (including red blood cells (RBC) count, hematocrit, Chloride, lactic acid dehydrogenase, prothrombin time, etc) with normal range and are not CTCAE gradable. The shift of these tests from baseline low/normal/high to lowest/highest post-baseline will be prepared.

The number and percentage of patients with elevated AST, ALT, total bilirubin, and alkaline phosphatase will be summarized for safety analysis set. Elevations will be summarized as a function of the ULN.

- $3 \times \text{ULN}$, $5 \times \text{ULN}$, $10 \times \text{ULN}$, and $20 \times \text{ULN}$ elevations of AST, ALT, and either ALT or AST.
- $>1.5 \times \text{ULN}$ and $>2 \times \text{ULN}$ elevations of Total bilirubin.
- Any elevations of ALP $>1.5 \times \text{ULN}$.
- Elevation of ALT/AST ($>3 \times \text{ULN}$) accompanied by Total bilirubin ($>1.5 \times \text{ULN}$, $>2 \times \text{ULN}$).

A separate listing will also be provided for all hematology, coagulation, clinical chemistry (including thyroid function tests) and urinalysis. Laboratory values that are outside the normal range will also be flagged in the data listings, along with corresponding normal ranges. Any out-of-range values that are identified by the investigator as being clinically significant will also be shown in the data listing.

For all NCI-CTCAE programmatically gradable laboratory tests, separate listings will be provided for all Grade 3 or higher abnormal lab results (in either direction) together with corresponding baseline results.

9.6. **Electrocardiograms (ECG)**

For triplicate ECG measurements, the mean of all assessments at each scheduled time point will be used for descriptive summarization purpose; however, all ECG measurements will be provided in data listings.

Local-read ECG data will be listed overall and a separate listing for any clinically significant finding in ECG values will be provided.

Absolute and CFB values for PR Interval, QT Interval, QTcF, QRS Duration and HR will be summarized descriptively by visit and by dose level in escalation phase and by arm in expansion phase. QTcF will be calculated with $\text{QT}/(\text{RR})^{1/3}$.

The frequency and percentage of subjects will be tabulated descriptively for the following:

- Highest post-baseline QTcF >450 msec
- Highest post-baseline QTcF >480 msec
- Highest post-baseline QTcF >500 msec
- Maximum CFB of QTcF > 30 msec
- Maximum CFB of QTcF > 60 msec

9.7. **Vital Signs and Body Measurements**

The absolute values of vital sign and body measurements (including weight, systolic blood pressure, diastolic blood pressure, HR, and temperature) and the CFB measurements will be summarized descriptively for each analysis group over scheduled time points (visits) as defined in Subsection 6.2.

QMS Document Name: Statistical Analysis Plan Template(EN)	Page 26 of 41
QMS No (include version ref): STF-015-GL.03	Document date: 14JUL2022
CONFIDENTIAL	

The number and percentage of patients with the following notably abnormal vital signs and body measurements will be presented by visit:

- Clinically notable elevated values:
 - Systolic BP: ≥ 180 mmHg and an increase ≥ 20 mmHg from baseline
 - Diastolic BP: ≥ 105 mmHg and an increase ≥ 15 mmHg from baseline
 - Weight: Increase of $\geq 10\%$ from baseline
 - Heart rate: ≥ 120 bpm with an increase of ≥ 15 bpm from baseline
 - Temperature: $> 38^\circ\text{C}$
- Clinically notable decrease values:
 - Systolic BP: ≤ 90 mmHg and a decrease ≥ 20 mmHg from baseline
 - Diastolic BP: ≤ 50 mmHg and a decrease ≥ 15 mmHg from baseline
 - Weight: decrease of $\geq 10\%$ from baseline
 - Heart rate: ≤ 50 bpm and a decrease ≥ 15 bpm from baseline
 - Temperature: $< 35^\circ\text{C}$

Vital signs will be provided in a data listing by subject using the Safety Analysis Set.

9.8. Physical Examination

Any clinically significant findings at Screening should be reported on the Medical History; otherwise, new/worsened clinically significant findings should be reported as Adverse Events.

All physical examination data will be listed.

9.9. ECOG Performance Status

ECOG performance status will be provided in a data listing.

9.10. Pregnancies

Pregnancy test results will be provided in a data listing using the Safety Analysis Set.

10. Pharmacokinetics

10.1. Schedule for PK Sampling

On Cycle 1 Day 1~ Day 8 and Cycle 2 Day 1 ~ Day 8 of Dose Escalation, the samples will be collected at Pre-dose, Immediately after (± 5 minutes) WTX-330 infusion, 4 hours (± 30 minutes) post start of WTX-330 infusion, 8 hours (± 30 minutes) post start of WTX-330 infusion, 24 hours (± 2 hours) post start of WTX-330 infusion, 48 hours (± 2 hours) post start of WTX-330 infusion, 168 hours (± 4 hours) post start of WTX-330 Infusion. On other visits, the samples will be collected at Pre-dose, Immediately after (± 5 minutes) WTX-330 infusion. On Dose Expansion, the samples will be collected at Pre-dose, Immediately after (± 5 minutes) WTX-330 infusion.

10.2. Pharmacokinetic Parameters

Plasma concentrations of WTX-330 and free IL-12 will be determined with a validated bioanalytical assay. PK parameters for WTX-330 and free IL-12 at Cycle 1 and Cycle 2 of Dose Escalation will be calculated from plasma concentrations using noncompartmental analyses: C_{\max} , T_{\max} , $t_{1/2}$, AUC_{0-14d} .

QMS Document Name: Statistical Analysis Plan Template(EN)	Page 27 of 41
QMS No (include version ref): STF-015-GL.03	Document date: 14JUL2022
CONFIDENTIAL	

10.3. Analysis of Pharmacokinetic Parameters

The PK Analysis Set will be used for summaries of all PK data.

WTX-330 and free IL-12 plasma concentrations will be summarized by visit and dose cohort (n, mean, geometric mean, standard deviation, coefficient of variation, median, Min and Max).

C_{max} , T_{max} , $t_{1/2}$, AUC_{0-14d} at Cycle 1 and Cycle 2 will be summarized with descriptive statistics (n, mean, geometric mean, standard deviation, coefficient of variation, median, Min and Max). T_{max} will be summarized with descriptive statistics (n, mean, standard deviation, median, Min and Max).

[figure not shown]
Plots of mean WTX-330 and free IL-12 plasma concentrations versus time will be generated by dose group and phase in linear and semi-logarithmic form. Individual plasma concentrations versus time graphs will also be provided.

11. Anti-Drug Antibody (ADA)

[figure not shown]
[figure not shown]
ADA Samples will be collected at pre-dose on each schedule and unscheduled visit.

Anti-drug antibody (ADA) data of WTX-330 will be provided in listing. ADA will be summarized in tabular by visit under the following categories:

- N (%) of patients with ADA at baseline (i.e. ADA detectable in the Cycle 1 Day 1 pre-dose sample)
- N (%) of patients with post-dose ADA (i.e. ADA detectable in any pre-dose sample from Cycle 1 Day 15 and later)
- N (%) of patients with treatment-induced ADA, defined as those patients with no ADA at baseline and one or more post-treatment (Cycle 1 Day 15 and later) ADA-positive sample.
- N (%) of patients with treatment-boosted ADA, defined as patients with a positive baseline ADA result who had one or more post-treatment (Cycle 1 Day 15 and later) ADA result with a higher titer than that of the baseline ADA sample.
- N (%) of patients with treatment-unaffected ADA, defined as patients with a positive baseline ADA result who had post-treatment (Cycle 1 Day 15 and later) ADA result with a lower titer than that of the baseline ADA sample.

QMS Document Name: Statistical Analysis Plan Template(EN)	Page 28 of 41
QMS No (include version ref): STF-015-GL.03	Document date: 14JUL2022
CONFIDENTIAL	

QMS Document Name: Statistical Analysis Plan Template(EN)	Page 29 of 41
QMS No (include version ref): STF-015-GL.03	Document date: 14JUL2022
CONFIDENTIAL	

QMS Document Name: Statistical Analysis Plan Template(EN)	Page 30 of 41
QMS No (include version ref): STF-015-GL.03	Document date: 14JUL2022
CONFIDENTIAL	

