1.2. Study Objectives and Endpoints

Objectives	Outcome Variables
Primary Objectives and Endpoints for Dose Escalation	

 To determine the MTD and/or recommended dose for expansion (RDE). 	
 Frequency, severity, and relatedness of treatment-emergent adverse events (TEAEs) and serious adverse events (SAEs), changes in safety laboratory parameters, and DLTs (if observed) for WTX- 330.
Dose Escalation and Expansion (Parts 1 and 2)	

 To further characterize the safety of WTX- 330 	
 Frequency, severity, and relatedness of TEAEs and SAEs, changes in safety laboratory parameters, and DLTs (if observed) for WTX-330

 To evaluate the anti-tumor activity of WTX-330 	
 Overall response rate (ORR) (complete response [CR] + partial response [PR]), duration of response (DOR) by Response Evaluation Criteria in Solid Tumors (RECIST) 1.1 and immune-overall response rate (iORR) (immune-complete response [iCR] + immune-partial response [iPR]) by immune-RECIST (iRECIST), or response by Lugano criteria (for lymphoma only)
Secondary Objectives and Endpoints (Parts 1 and 2)	
	
	

 To evaluate the immunogenicity of WTX330 	
 Incidence and titers of ADAs towards WTX-330

QMS Document Name: Statistical Analysis Plan Template(EN)	Page 6 of 41
QMS No (include version ref): STF-015-GL.03	Document date: 14JUL2022
CONFIDENTIAL	

Objectives	Outcome Variables
Secondary Objectives and Endpoints (Parts 2)	

 To evaluate the antitumor activity of WTX-330 in patients with relapsed/refractory (r/r) advanced or metastatic malignancies who have progressed on CPIs or who have tumor indications for which CPIs are not approved 	
 ORR (CR + PR) based on best overall response (BOR) DOR Disease control rate at month 3, 6 and 9 Progression free survival (PFS) per RECIST v1.1 (solid tumor) and iRECIST or Lugano classification (lymphoma; Cheson et al., 2014) assessed by Investigator. Overall survival (OS)
Exploratory Objectives and Endpoints (Parts 1 and 2)	

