T_{max} and T_{last} summary will no include Geometric Mean, Coefficient of variation

The following table will be displayed as Table 14.4.2.1,

Table 14.4.2.2

Summary of Free IL-12 Pharmacokinetic Parameters
 Pharmacokinetic Analysis Set

Programming Note:

Units for Free IL-12, use pg/ml - multiply vendor conc by 1000

Table 14.4.3.1
 Summary of Anti-drug Antibody for WTX-330 - Dose Escalation and **Dose Expansion**
 Anti-Drug Antibody Analysis Set

	WTX-330 0.016 mg/kg (N=x)	WTX-330 0.032 mg/kg (N=x)	WTX-330 0.056 mg/kg (N=x)	WTX-330 0.084 mg/kg (N=x)	WTX-330 0.126 mg/kg (N=x)	WTX-330 0.190 mg/kg (N=x)	WTX-330 0.290 mg/kg (N=x)	WTX-330 0.XXX mg/kg (N=x)	Total (N=xX)
ADA at Baseline, n(%)									
Positive	X (XX.X)	X (XX.X)	X (XX.X)	XX (XX.X)	XX (XX.X)	XX (XX.X)	XX (XX.X)	XX (XX.X)	XX (XX.X)
Negative	X (XX.X)	X (XX.X)	X (XX.X)	XX (XX.X)	XX (XX.X)	XX (XX.X)	XX (XX.X)	XX (XX.X)	XX (XX.X)
Unknown	X (XX.X)	X (XX.X)	X (XX.X)	XX (XX.X)	XX (XX.X)	XX (XX.X)	XX (XX.X)	XX (XX.X)	XX (XX.X)
ADA at Post-Baseline, n(%)									
At least one positive	X (XX.X)	X (XX.X)	X (XX.X)	XX (XX.X)	XX (XX.X)	XX (XX.X)	XX (XX.X)	XX (XX.X)	XX (XX.X)
All negative	X (XX.X)	X (XX.X)	X (XX.X)	XX (XX.X)	XX (XX.X)	XX (XX.X)	XX (XX.X)	XX (XX.X)	XX (XX.X)
Unknown	X (XX.X)	X (XX.X)	X (XX.X)	XX (XX.X)	XX (XX.X)	XX (XX.X)	XX (XX.X)	XX (XX.X)	XX (XX.X)
Treatment-induced ADA, n(%)									
Treatment-boosted ADA, n(%)	X (XX.X)	X (XX.X)	X (XX.X)	XX (XX.X)	XX (XX.X)	XX (XX.X)	XX (XX.X)	XX (XX.X)	XX (XX.X)
Treatment-unaffected ADA, n(%)	X (XX.X)	X (XX.X)	X (XX.X)	XX (XX.X)	XX (XX.X)	XX (XX.X)	XX (XX.X)	XX (XX.X)	XX (XX.X)

Note: Treatment-induced ADA is defined as those patients with no ADA at baseline and one or more post-treatment (Cycle 1 Day 15 and later) ADA-positive sample. Treatment-boosted ADA is defined as patients with a positive baseline ADA result who had one or more post-treatment (Cycle 1 Day 15 and later) ADA result with a higher titer than that of the baseline ADA sample. Treatment-unaffected ADA, defined as patients with a positive baseline ADA result who had post-treatment (Cycle 1 Day 15 and later) ADA result with a lower titer than that of the baseline ADA sample in all visits.

Note: Dose escalation and dose expansion are summarized together by dose level.

Programming Note:

Combine Dose Escalation and Dose Expansion and summary the results by dose level

[figure not shown]
[figure not shown]
Protocol: WTX-330x2101

Date: 26Feb2025

Figure Shells

Figure 14.4.1.1.1

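### Treatment-unaffected ADA is defined as a titer below baseline, so a baseline-positive patient with an unchanged titer is neither boosted nor unaffected, and SAP Section 11 and the Table 14.4.3.1 footnote differ on the rule

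*SAP*

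**What the plan says.** The SAP's table of objectives and endpoints (Section 1.2) lists immunogenicity as a secondary objective, with the endpoint "Incidence and titers of ADAs towards WTX-330". Section 11 sets out the categories:

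- **Treatment-induced:** "patients with no ADA at baseline and one or more post-treatment (Cycle 1 Day 15 and later) ADA-positive sample". This applies only to patients who are negative at baseline.
- **Treatment-boosted:** positive at baseline, with "one or more post-treatment (Cycle 1 Day 15 and later) ADA result with a higher titer than that of the baseline ADA sample".
- **Treatment-unaffected:** positive at baseline, with a post-treatment "ADA result with a lower titer than that of the baseline ADA sample".

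Section 11 also plans repeated sampling: "ADA Samples will be collected at pre-dose on each schedule and unscheduled visit". It says that "ADA will be summarized in tabular by visit under the following categories", although the categories themselves describe patients.

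The shell for Table 14.4.3.1 has one block per patient with no visit dimension. Its footnote repeats the induced and boosted definitions, but for unaffected it requires an "ADA result with a lower titer than that of the baseline ADA sample in all visits". The table also has rows for ADA at baseline (positive, negative, unknown) and at post-baseline (at least one positive, all negative, unknown).

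**The concern.** Boosted and unaffected are the only two treatment-effect categories open to a baseline-positive patient. One needs a titer above baseline and the other a titer below it. Neither covers a titer equal to baseline, which is the plainest case of a patient whose antibodies treatment did not affect.

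The two texts also give different rules. Section 11 does not say whether one lower result is enough or whether all must be lower; the footnote says all. A programmer has to choose between them, and the same patient can be classed differently depending on the choice. Boosted plus unaffected then need not equal the number of baseline-positive patients with follow-up samples, and a reader of the table could not tell why.

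Table 14.4.3.1 is the only ADA summary table in the shells' list of tables, so no other planned table would show the discrepancy.

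**Working it through.** The plan gives no figure to reproduce here. The check is logical: list every way the post-treatment titers of a baseline-positive patient can compare with baseline, and see which rows apply.

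**Inputs.** Each post-treatment result (Cycle 1 Day 15 or later) is H (higher than baseline), E (equal) or L (lower). With k results there are 3^k patterns. Repeated samples per patient come from the sampling rule in SAP Section 11.

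**Rules compared.**

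- Boosted, in both texts: at least one H.
- Unaffected (a), Section 11 read as any lower result: at least one L.
- Unaffected (b), footnote: every result is L.
- Unaffected (c), proposed: no H.

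**Counting.**

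- Under (a), a pattern is unclassified if it has no H and no L, so only all-E qualifies: 1 pattern for any k. It is in both rows if it has at least one H and at least one L: 3^k − 2·2^k + 1. For k = 1, 2, 3 this gives 3 − 4 + 1 = 0, 9 − 8 + 1 = 2 and 27 − 16 + 1 = 12.
- Under (b), a pattern is unclassified if it has no H and is not all L: 2^k − 1, that is 1, 3 and 7. None is in both rows, because all-L excludes any H.
- Under (c), unaffected is the complement of boosted, so every pattern falls in exactly one row.

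| Post-treatment results | Patterns | (a) neither row | (a) both rows | (b) neither row | (b) both rows | (c) exactly one row |
|---|---|---|---|---|---|---|
| 1 | 3 | 1 (E) | 0 | 1 (E) | 0 | 3 |
| 2 | 9 | 1 (EE) | 2 (HL, LH) | 3 (EE, EL, LE) | 0 | 9 |
| 3 | 27 | 1 | 12 | 7 | 0 | 27 |

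**By-visit reading.** If Section 11 is applied separately at each visit, a single result cannot be both higher and lower, so there is no overlap at that visit. An equal titer at that visit still belongs to neither category.

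**ADA-negative and missing follow-up.** Neither text says how to class a baseline-positive patient whose later samples are ADA-negative and so have no titer. The ADA Analysis Set (SAP Section 5) admits patients with a baseline sample or a post-baseline sample, so a baseline-positive patient with no later sample can be in the set. The post-baseline *Unknown* row can hold that patient.

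**The case against.** Four points can be made on the other side.

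1. **The patients do not disappear.** A reader might infer that patients with an unchanged titer are missing from the table altogether. They are not. Such a patient is counted as positive at baseline and, the titer being unchanged, as having at least one positive result post-baseline. The patient is absent only from the boosted and unaffected rows. This point stands and limits the finding.

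2. **The planned table does not count patients twice.** A reader might infer that it does. The footnote requires a lower titer at all visits, which excludes every boosted patient. The SAP and the shells are both version 2.0 of 26 February 2025, so the footnote is current text. Overlap arises only if Section 11 is read per patient and as any lower result, a qualifier it does not state. This stands too. What remains is a conflict between two current texts, and the footnote avoids overlap only by leaving more patterns unclassified.

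3. **Nothing says that boosted and unaffected must add up to baseline-positive.** That is true, and some shortfall is inherent because a patient may have no later sample. It does not explain leaving out patients who have later samples and an unchanged titer.

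4. **Little depends on it.** The endpoint is descriptive, SAP Section 13 plans no formal testing of efficacy or safety endpoints, the ADA results will also be listed, and no decision rule in the documents uses these categories. This stands and sets the size of the point.

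No other section supplies the missing equal-titer case. Redaction does not explain it, since both definitions can be read in full.

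**Conclusion.** The definition is wrong as written, in a limited way. Under both SAP Section 11 and the Table 14.4.3.1 footnote, a baseline-positive patient whose titer stays equal to baseline is in neither treatment-effect row. This does not depend on how Section 11 is read. The conflict between the two texts is equally certain. Its consequence depends on the text followed: the footnote leaves mixed equal and lower patients unclassified, while Section 11 read as any lower result lets a patient with one higher and one lower titer count twice.

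The fractions in the table above count patterns and are not patient frequencies. A reader might want a number of affected patients, but the documents give neither the prevalence of ADA at baseline nor the share of titers that would stay unchanged, so any such number would be a guess.

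The effect is confined to how a descriptive secondary endpoint is presented. Sample size, error rates and the primary analyses are untouched. This is a minor wording correction, worth making before the table is programmed.

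**What to change.** In SAP Section 11 and in the footnote to Table 14.4.3.1, use one definition of treatment-unaffected ADA: positive at baseline, at least one post-treatment result (Cycle 1 Day 15 or later), and no post-treatment titer above baseline, meaning equal, lower or ADA-negative at all visits.

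Boosted and unaffected are then mutually exclusive. They are exhaustive among baseline-positive patients with a post-treatment result, but not among all baseline-positive patients: those with no later result stay in the post-baseline *Unknown* row, and the footnote should say so. Section 11 should also state that these categories are assigned per patient across visits, to match the layout of the shell.

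The cost is about one line in each of two places. No new data, samples or analyses are needed.
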